#### 5.3. INTENT-TO-TREAT POPULATION (ITT)

The ITT population will include all patients from the safety population. However, due to the different study designs, the patients enrolled from CVT-301-003 and CVT-301-009 will not be included in efficacy summaries (i.e. the patients enrolled from CVT-301-003 and CVT-301-009 will be excluded from ITT population). The rationale for excluding the CVT-301-003 patients from the efficacy summaries is the gap between the end of CVT-301-003 and start of CVT-301-004E. The rationale for excluding the CVT-301-009 patients from the efficacy summaries is the study design (single-dose study) which is not comparable to the design of the rest of the studies. Patients will be analyzed according to randomized treatment group. The ITT Population will be used for all analyses of efficacy endpoints and summaries of patient demographic and baseline disease characteristics.

In case of variables which are not captured throughout the whole study but only added after an protocol amendment (e.g. PHQ-9), the ITT population for the variable in question includes only the subset of the ITT population in which at least the baseline and one post-baseline assessment of the variable in question were done.

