10.1.4. Sub-Study to Assess Potential Withdrawal Symptoms

After patients are consented to protocol Version 5.2, they will participate in a withdrawal symptom sub-study at the end of TV4, TV5, or TV6, depending on which of the visits is the next scheduled one for the patient. In addition to the assessments detailed in the previous sections for the treatment visit, the AWQ and DDS-PC will be performed upon arrival in the ON state, and the UPDRS Part 1 will be performed preferably in the ON state.

When study activities for the visit are completed, patients will begin a 28-day period of assessment of potential drug withdrawal symptoms. To this end, patients who are at TV4 or TV5 at the time of consent will go on a study drug holiday for this time period. All patients in the withdrawal sub-study (patients consented to protocol Version 5.2) will be given copies of the AWQ, the DDS-PC, PHQ-9, Epworth Sleepiness Scale, C-SSRS (self-report version), and the self-administered MDS-UPDRS Parts 1B and 2 (Movement Disorder Society -UPDRS) to be completed at home at 1, 3, 6, 8, 11, 14, 17, 24, and 28 days after the treatment visit. Patients should fill out the questionnaires during their first ON state (after the intake of their first scheduled dose of standard oral PD medication) on each of these days. The site will call patients

at 14 (± 3) days after the treatment visit to remind them to complete the questionnaires, and to inquire about potential adverse events and changes in concomitant medications. Patients who enter the withdrawal sub-study after TV6 will also receive a call at 28 (± 3) days.

Patients who entered the study drug holiday will be scheduled to return to the clinic for a drug re-supply visit (see [Section 10.1.4.1](#)), and resumption of the full course of study treatment. Patients who entered the withdrawal sub-study after TV6 will be completed with the study after they return the questionnaires and undergo the DLco and spirometry assessment 4 to 5 weeks after completion of TV6, as described in [Section 10.1.3.9](#).

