- ECG: HR, PR, QRS, QT and RR intervals, QTcB (Bazett’s correction formula calculated as $QT/RR^{1/2}$) and QTcF (Fridericia’s correction formula calculated as $QT/RR^{1/3}$). ECG parameter values or parameter changes of potential clinical concern will be tabulated.
- Spirometry: FEV1, FVC, and the FEV1/FVC ratio during specified treatment visits and over the course of the study will be evaluated. The number and proportion of patients with pre-specified changes in spirometry parameters will be tabulated.
- Changes from baseline to follow-up in the rating scales for assessing suicidality, somnolence, and impulse control disorders will be summarized descriptively.
- For the AWQ, DDS-PC, PHQ-9, Epworth Sleepiness Scale, C-SSRS, and UPDRS Parts 1 and 2, the change from baseline to days 1, 3, 6, 8, 11, 14, 17, 24, and 28 of the withdrawal symptom assessment period will be summarized descriptively.

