## Statistical Analysis Plan

### Baseline

Baseline is defined as the last non-missing assessment before the first dose of CVT-301 in study CVT-301-004 for the patients who received CVT-301 in CVT-301-004 and as the last non-missing assessment before the first dose of CVT-301 in CVT-301-004E for the rest of the patients.

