## Statistical Analysis Plan

patients. This summary will be complemented by the distribution of each response category (much improved, improved, a little improved, no change, a little worse, worse, much worse) tabulated by the treatment group. The data will be summarized with descriptive statistics within each treatment group and overall.

- Changes from baseline in endpoints based on S&E ADL score, UPDRS Part 2 score, PHQ-9 total score, and PDQ-39 sub-scores and index score. An ANCOVA model with the treatment group, treatment/study group and stratification variables as fixed factors and the baseline value as a covariate will be used to estimate the treatment group differences. In addition, the data will be presented with descriptive statistics classified by treatment group and visit. The observed cases will be used in the analysis and summaries.
- Change from baseline (TV1) and Last Day of Treatment (LDOT) to days 1, 3, 6, 8, 11, 14, 17, 24, and 28 after TV6 in the PHQ-9 will be summarized descriptively. LDOT is defined as assessment taken on TV6 or ET for patients who didn't enrolled into the sub-study and TV4, TV5 or TV6 for patients who enrolled into sub-study.

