## Statistical Analysis Plan

Table 14.2.2.1.8	Efficacy Subgroup Analysis: Change from Baseline in Total Daily OFF Time by Treatment Group, Visit and Age Group (ITT Population)
Table 14.2.2.1.9	Efficacy Subgroup Analysis: Change from Baseline in Total Daily OFF Time by Treatment Group, Visit and Gender (ITT Population)
Table 14.2.2.2.1	Efficacy Analysis: Mean of Total Daily ON Time without Dyskinesia by Treatment Group and Visit (ITT Population)
Table 14.2.2.3.1	Efficacy Analysis: Mean of Total Daily ON Time with non-Troublesome Dyskinesia by Treatment Group and Visit (ITT Population)
Table 14.2.2.4.1	Efficacy Analysis: Mean of Total Daily ON Time with Troublesome Dyskinesia by Treatment Group and Visit (ITT Population)
Table 14.2.3.1	Efficacy Analysis: Subjects Global Impression of Change (PGI-C) by Treatment Group and Visit Worst Case Imputation [a] (ITT Population)
Table 14.2.4.1	Efficacy Analysis: UPDRS Part 2 Score by Treatment Group and Visit (ITT Population)
Table 14.2.4.2	Efficacy Analysis: Schwab and England (S&E) Activities of Daily Living (ADL) Score by Treatment Group and Visit (ITT Population)
Table 14.2.4.3	Efficacy Analysis: 39 Item Parkinson's disease Questionnaire (PDQ-39) Sub-scores and Summary Index Score by Treatment Group, Visit (ITT Population)
Table 14.2.4.4	Efficacy Analysis: 9-Item PHQ-9 Sum Score by Treatment Group and Visit (ITT Population)
Table 14.2.4.4.1	Change from Baseline (TV1) and Last Day of Treatment (LDOT) to Days 1, 3, 6, 8, 11, 14, 17, 24, and 28 after LDOT in PHQ-9 Total Score by Treatment Group (ITT Population)
Table 14.2.4.5.1	Efficacy Analysis: Impact of Parkinson's OFF Episodes Patient Survey Score by Treatment Group and Visit (ITT Population)
Table 14.2.4.5.2	Exploratory Efficacy Analysis: Frequency of Impact of Parkinson's OFF Episodes Patient Survey by Treatment Group and Visit (ITT Population)
Table 14.3.1.1.1	Extent of Exposure: Overall Exposure by Treatment Group (Safety Population)
Table 14.3.1.1.2	Extent of Exposure: Overall Exposure by Treatment/Study (ITT Population)
Table 14.3.1.2.1	In-Clinic Study Drug Administration by Treatment Group (Safety Population)
Table 14.3.1.2.2	In-Clinic Study Drug Administration by Treatment/Study (ITT Population)
Table 14.3.1.3.1	Distribution of Time of Study Drug Administration by Treatment Group (Safety Population)
Table 14.3.1.3.2	Distribution of Time of Study Drug Administration by Treatment/Study (ITT Population)

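### The PHQ-9 withdrawal summary is run only in the efficacy ITT population, which as written drops 003 and 009 rollovers and patients without a baseline PHQ-9 who may have usable withdrawal scores

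*SAP*

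**What the plan says.** **Protocol.** Section 12.5 (Safety Analysis) plans one descriptive withdrawal summary for several instruments together: "For the AWQ, DDS-PC, PHQ-9, Epworth Sleepiness Scale, C-SSRS, and UPDRS Parts 1 and 2". The synopsis repeats this under its safety analyses. Protocol 12.2 defines the safety set as every enrolled patient with at least one dose. Section 10.1.4 says of patients consented to Version 5.2 that "they will participate in a withdrawal symptom sub-study at the end of TV4, TV5, or TV6", and they then complete the PHQ-9 at home on nine days up to Day 28.

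**SAP.** The PHQ-9 withdrawal summary stands in the efficacy section. SAP 8.1 assigns its analyses to the ITT population and says that changes from baseline (TV1) and from LDOT to Days 1 through "24, and 28 after TV6 in the PHQ-9 will be summarized descriptively". The title of Table 14.2.4.4.1 ends "in PHQ-9 Total Score by Treatment Group (ITT Population". SAP 5.3 sets two limits on that population. First, "the patients enrolled from CVT-301-003 and CVT-301-009 will be excluded from ITT population". Second, for variables not collected throughout the study, with the PHQ-9 as the named example, the population "includes only the subset of the ITT population in which at least the baseline and one post-baseline assessment" of the variable exist.

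The other withdrawal tables are all labelled Safety Population in the table index: self-report C-SSRS (14.3.4.6.3), Epworth (14.3.4.7.1), AWQ (14.3.4.11), DDS-PC (14.3.4.12) and MDS-UPDRS (14.3.4.13.1 and 14.3.4.13.2). The index has no Safety Population version of the PHQ-9 withdrawal table.

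**The concern.** Change in mood after stopping CVT-301 is one of the things the withdrawal assessments are meant to detect. The SAP gives reasons for the 003 and 009 exclusions: the gap before entry to CVT-301-004E for 003, and the single-dose prior design for 009. Both concern comparability of efficacy results and have no evident bearing on symptoms in the four weeks after the last dose. The baseline requirement makes sense for change from start of treatment, but change from LDOT does not use that value.

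The result is that a protocol safety summary is reported on a narrower set of patients than its companion measures. The columns can differ too, because ITT groups by randomised treatment and Safety by highest dose level received. A reader comparing PHQ-9 with AWQ or Epworth over the same 28 days would not be looking at the same patients.

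**Working it through.** There is no stated figure to reproduce, so the check traces patients through the rules.

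**1. What the LDOT change needs.** Change on Day d = PHQ-9 on Day d minus PHQ-9 at LDOT, for d = 1, 3, 6, 8, 11, 14, 17, 24, 28. No TV1 or pre-treatment value enters.

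**2. Who is kept.** Take patients who all have an LDOT score and Day 1 to 28 scores.

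| Patient | AWQ, DDS-PC, Epworth, MDS-UPDRS, C-SSRS withdrawal tables (Safety) | PHQ-9 withdrawal table (ITT) |
|---|---|---|
| Naïve, 005 observational arm or 004 placebo, with a PHQ-9 at TV1 of 004E | In | In |
| 003 rollover | In | Out, SAP 5.3 |
| 009 rollover, even with a PHQ-9 at TV1 of 004E | In | Out, SAP 5.3 |
| Naïve, 005 or 004 placebo, whose TV1 preceded PHQ-9 collection | In | Out, if baseline means before first dose |
| 004 active-arm patient | In | Depends on which baseline applies (step 4) |

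Former 003 patients can reach the withdrawal period, because Protocol 7 re-consents those already enrolled.

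**3. Contrast with instruments added later.** The SAP's own change summary shows AWQ and DDS-PC entering with version 2.0. SAP 9.14 and 9.15 summarise both in the Safety Population with no baseline requirement. The amendment rule in SAP 5.3 applies only to ITT variables, so among the withdrawal measures it affects the PHQ-9 alone.

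**4. Which baseline.** The documents give three answers.
- SAP 6.2: "Baseline is defined as the last non-missing assessment before the first dose of CVT-301 in study CVT-301-004" for patients on active drug there, and before the first dose in 004E for the rest.
- SAP 4.2 and 8.1 refer to TV1. Protocol 10.1.3.2 has 004 patients complete a PHQ-9 at TV1 of 004E, which for the active arm comes after exposure.
- Protocol 12.3 exempts withdrawal assessments from the treatment-start baseline but does not say what replaces it.

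The 003 and 009 exclusion does not depend on this choice. The missing-baseline exclusion does.

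**5. Two further mismatches.** SAP 6.3 describes the Safety and ITT populations as all dosed patients regardless of post-baseline data, which does not fit SAP 5.3. SAP 8.1 counts days after TV6, while Table 14.2.4.4.1 counts days after LDOT. For patients whose withdrawal period follows TV4 or TV5 these are different dates.

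**6. Size.** The documents give planned totals (about 390 enrolled, about 290 completing). They give no count of 003 or 009 rollovers in the withdrawal period, no date on which PHQ-9 collection began, and no count of patients without a baseline score. The number excluded cannot be computed.

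**The case against.** The PHQ-9 is a secondary objective and an efficacy criterion in both documents, so an ITT default follows from its class. The SAP states that it supersedes the protocol where they differ, and SAP 11 discloses the 003 and 009 exclusion. The withdrawal table is purely descriptive, with no test or threshold attached. If the withdrawal baseline is the last on-treatment visit, as Protocol 12.3 permits, a patient with LDOT and later scores already meets the SAP 5.3 condition.

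Much of this stands. Efficacy placement is reasonable for the on-treatment PHQ-9, and no planned decision depends on this table. But SAP 11 discloses the exclusion for efficacy summaries only; it does not say that a protocol safety summary was moved onto the efficacy set. The Protocol 12.3 reading could rescue patients without a baseline score, but not the 003 and 009 rollovers. SAP 8.1 also names TV1 as the baseline and LDOT as a separate reference, which favours the restrictive reading.

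Three stronger inferences are tempting and unsupported:
- **That depression after stopping goes unexamined.** Patients outside 003 and 009 with a baseline score are summarised. All individual PHQ-9 scores appear in Listing 16.2.6.3.4 (All Available Population), and adverse events and C-SSRS are summarised in the Safety Population.
- **That the PHQ-9 arrived with Version 5.2, so most sub-study patients lack a baseline.** No document dates its introduction. The SAP change summary adds only the Day 1 to 28 analysis for the PHQ-9, which suggests that collection began earlier.
- **That all 004 active-arm patients drop out.** This requires both a literal SAP 6.2 baseline and no PHQ-9 in study 004. The documents do not say whether 004 collected it.

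**Conclusion.** The point holds in a limited form. As written, the only PHQ-9 withdrawal summary excludes 003 and 009 rollovers and, on the more natural reading of the SAP, anyone without a baseline PHQ-9, whether or not LDOT and Day 1 to 28 scores exist. Every parallel withdrawal table uses the Safety Population, and the protocol planned this summary as a safety analysis. The exclusion of 003 and 009 patients rests on explicit text. The exclusion for a missing baseline rests on taking SAP 5.3 with SAP 6.2 or the TV1 label rather than with the Protocol 12.3 exemption.

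The effect is of unknown size and may be small. I put no percentage or loss of precision on it, because any such figure would rest on an exclusion rate that the documents do not supply. The case for changing the plan is that usable patients return to a planned safety summary at almost no cost.

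**What to change.** 1. Produce Table 14.2.4.4.1 in the Safety Population, grouped as the other withdrawal tables are.
2. In the change-from-LDOT rows, include every patient with an LDOT PHQ-9 and at least one PHQ-9 on Days 1 to 28, whether or not a TV1 score exists. Use TV1 only for the change-from-TV1 rows, and show the n for each.
3. State in SAP 5.3 that the amendment-variable rule does not apply to withdrawal summaries, and reconcile it with SAP 6.3.
4. State one withdrawal baseline, reconciling Protocol 12.3 with SAP 6.2 and the TV1 label in SAP 4.2 and 8.1.
5. Change the SAP 8.1 day count from TV6 to LDOT to match the table. The LDOT shift table in SAP 9.9 carries the same wording.
6. Record the change of population in SAP 11.

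The cost is SAP wording and one population flag. No new data are needed and trial conduct does not change. Moving the table into the safety numbering is optional.

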#### 5.4. PROTOCOL DEVIATIONS

A protocol deviation is any significant finding indicating that the study investigator or patient failed to adhere to the protocol requirements (e.g., drug noncompliance, failure to return for defined number of visits or within an acceptable visit window for completion of study assessments). The deviation may necessitate premature termination of the patient from the visit assessments, or from the study.

1003804

Civitas Therapeutics, Inc.

CVT-301-004E

SAP Version 2.0

## Statistical Analysis Plan

The deviations will be classified during a blind review process with the Sponsor and other study personnel (as appropriate) before database lock. The deviations will be classified as minor or major during a blind review process. All decisions regarding major/minor deviations will also be discussed between the Sponsor, other study personnel (as appropriate), and the study statistician prior to commencing the final analysis on the locked database.

The number of subjects with protocol deviations will be summarized by treatment group and overall. All protocol deviations will be listed.

## Statistical Analysis Plan

### 6. GENERAL ASPECTS FOR STATISTICAL ANALYSIS

#### 6.1. GENERAL METHODS

All patient data will be included in listings. All patients entered into the database will be included in patient data listings. The listings will be generally sorted by the study (and treatment) from which the patient was enrolled, Patient ID (and by visit and by time point, if applicable) within treatment group, unless specified otherwise.

All applicable data will be summarized by treatment group (CVT-301 DL1, CVT-301 DL2, CVT-301 overall) in tables, unless specified otherwise. Furthermore, selected summaries will be broken down into three groups as follows: patients who received CVT-301 in CVT-301-004 study, patients who received placebo in CVT-301-004 study and CVT-301 naïve patients (including CVT-301-005 observational arm patients) (referred to as “treatment/study group” in the SAP). The efficacy data from patients who were enrolled in the CVT-301-003 or CVT-301-009 study will be analyzed separately, as data listings. In addition, a patient disposition table will be provided for CVT-301-003 and CVT-301-009 patients. Where appropriate, data will be summarized by visit and/or time point in addition to treatment group. Unscheduled or repeat assessments will not be included in summary tables, but will be included in listings.

Continuous variables will be summarized using the number of observations (n), mean, SD, median, minimum, and maximum. Standard error of the mean (SEM) will also be provided for summaries of spirometry and efficacy endpoints, if relevant. The same number of decimal places as in the raw data will be presented when reporting minimum and maximum, 1 more decimal place than in the raw data will be presented when reporting mean and median, and 2 more decimal places than in the raw data will be presented when reporting SD and SEM.

Descriptive statistics for categorical/qualitative data will include frequency counts and percentages. The total number of patients in each treatment group/overall (N) will be used as the denominator for percent calculations, unless stated otherwise in the table shell. All percentages will be presented with one decimal point, unless specified otherwise. Percentages equal to 100 will be presented as 100% and percentages will not be presented for zero frequencies.

Significance testing will be 2-tailed using  $\alpha = 0.05$ , unless otherwise specified. All analyses and summaries will be produced using SAS® version 9.3 (or higher).

Deviations from the statistical plan will be reported in the clinical study report, including the rationale for use and information on whether the deviation was done before or after the blind of study CVT-301-004E was broken.

## Statistical Analysis Plan

### 6.2. KEY DEFINITIONS

#### Age

Age, as an integer, will be calculated using the date of birth and baseline date.

$$\text{Age} = \text{int} ((\text{baseline date} - \text{date of birth})/365.25)$$

#### Body Mass Index (BMI)

BMI will be calculated as follows and rounded to 1 decimal place:

$$\text{BMI (kg/m}^2\text{)} = \text{weight (kg)} / [\text{height (m)}]^2$$

#### Parkinson 's disease History

The following parameters will be calculated for the PD history:

$$\begin{aligned} \text{Time since diagnosis of PD (months)} &= \\ \text{Baseline Date (M/Y)} - \text{Date of diagnosis (M/Y)} \end{aligned}$$

$$\begin{aligned} \text{Duration of levodopa treatment (months)} &= \\ \text{Baseline Date (M/Y)} - \text{Start date of levodopa treatment (M/Y)} \end{aligned}$$

$$\begin{aligned} \text{Time since onset of wearing off episodes (months)} &= \\ \text{Baseline Date (M/Y)} - \text{Date of onset of wearing off episodes (M/Y)} \end{aligned}$$

For the definition of baseline data, see below. If the month is missing, the first month of the year will be used.

#### Change from pre-dose to post-dose

The change from pre-dose to post-dose within each visit will be calculated for each post-dose assessment as:

$$\text{Change from Pre-dose to Post-dose} = \text{Post-dose value} - \text{Pre-dose value}$$

#### Percent change from pre-dose to post-dose

The percent change from pre-dose to post-dose within each visit will be calculated for each post-dose assessment as:

$$\begin{aligned} \text{Percent Change from Pre-dose to Post-dose} &= \\ (\text{Post-dose value} - \text{Pre-dose value}) * 100 / \text{Pre-dose value} \end{aligned}$$

## Statistical Analysis Plan

### Baseline

Baseline is defined as the last non-missing assessment before the first dose of CVT-301 in study CVT-301-004 for the patients who received CVT-301 in CVT-301-004 and as the last non-missing assessment before the first dose of CVT-301 in CVT-301-004E for the rest of the patients.

